7.0 SUBJECT ASSESSMENTS

7.1 Clinical Assessments

Clinical assessments will take place according to the schedules depicted in the Study Calendars (Section 4.2) and will include complete histories and physical examinations. History and physicals may be obtained remotely. Additional visits may take place, and events that are noted at those visits (e.g., treatment-related toxicity) will be included in data analyses.

Adverse events will be scored at each clinic visit using CTCAE version 5.0. Any new or worsening toxicities will be classified as “unrelated” or “related” to study treatment (See Section 11.1). Adverse events will be documented in this manner for subjects on both study arms, so that adverse event rates with study therapy in Arm 1 can be compared to adverse event rates with standard therapy in Arm 2.

7.2 DLT Definition

The definition of a dose-limiting toxicity (DLT) will be nearly identical to the definition used in the recent study combining CDX-301 and CDX-1140⁷⁰. A DLT will be defined as any of the following outcomes, attributed to study therapy (including SBRT) and occurring within 8 weeks after initiation of initial study therapy:

- Death
- Any \geq Grade 3 non-hematological toxicity, with the following exceptions:
 - Grade 3 alopecia, vitiligo, or endocrinopathies controlled by hormone replacement therapy
 - Grade 3 nausea that resolves to \leq grade 2 with or without treatment within 72 hours
 - Grade 3 vomiting and diarrhea that resolves to \leq grade 2 with or without treatment within 72 hours
 - Grade 3 fatigue that resolves to \leq grade 2 within 5 days
 - Grade 3 hypertension in the absence of maximal medical therapy
 - Grade 3 adverse event of tumor flare (defined as local pain, irritation, or rash localized at sites of known or suspected tumor) of \leq 7 days in duration
 - Grade 3 amylase or lipase abnormalities that are not associated with symptoms or clinical manifestations of pancreatitis. It is recommended to consult with the Principal Investigator for grade 4 amylase or lipase abnormalities
 - Grade 3 clinically significant laboratory abnormalities that are asymptomatic and can be reversed within 72 hours, however:
 - Any Grade 4 ALT or AST elevation will be a DLT
 - Any Grade 3 ALT or AST elevation that lasts longer than 7 days will be a DLT
 - ALT or AST $> 8 \times$ ULN regardless of duration will be considered a DLT
 - ALT or AST $> 5 \times$ ULN that lasts longer than 14 days will be considered a DLT
 - ALT or AST of $> 3 \times$ ULN with a concurrent total bilirubin $> 2 \times$ ULN will be considered a DLT in the absence of another cause (other than study drug) of these elevations.
- Any of the following hematologic toxicities:
 - Grade 4 anemia (regardless of duration)
 - Grade 4 neutropenia persisting > 5 days
 - Grade 3 thrombocytopenia with hemorrhage
 - Grade 4 thrombocytopenia
 - Any other \geq Grade 3 hematologic adverse event not returning to baseline or \leq grade 1 prior to the next planned study drug dose, excluding asymptomatic lymphopenia which will not be considered a DLT
- \geq Grade 3 infusion reaction
 - Excluding grade 3 infusion reactions resolving within 6 hours with or without treatment
- \geq Grade 3 related injection site reaction will be considered a DLT and no further treatment with CDX-301 will be permitted
- Any \geq grade 2 eye pain or reduction of visual acuity that does not improve to \leq grade 1 severity within 2 weeks of the initiation of topical therapy or requires systemic treatment
- Treatment delay of > 2 weeks due to drug-related toxicity that is not improving will be considered a DLT.

7.3 Radiographic Assessments

Pre-registration imaging will be obtained prior to study entry and will consist of a whole-body PET/CT (within 42 days) and a diagnostic CT of the chest, abdomen, pelvis (within 21 days). The surveillance imaging schedule is detailed in the Study Calendars (Section 4.2) and includes CT of the chest, abdomen, and pelvis every 8 weeks for one year. CT imaging of the pelvis may be omitted for patients with no history of metastatic lesions in the anatomical area. Intravenous and oral contrast will be used, unless a contraindication to contrast administration exists. Additional imaging studies (e.g., FDG-PET, MRI) may be added at any time to assess disease that is not well-visualized on CT and/or if there is concern for disease progression. The surveillance imaging schedule beyond year 1 will be left to the discretion of the treating physicians but should follow current guidelines⁷⁵.

Subjects with a history of brain metastases will undergo surveillance for the development of new/progressive brain metastases. Imaging timing and details will be left to the discretion of the treating physicians but will generally follow current guidelines¹⁰⁷ and most often include high-resolution MRI of the brain with i.v. contrast every 2-3 months. Prompt MRI of the brain is recommended for any study subject who develops symptoms suggestive of new/worsening brain metastasis.

Tumor response and progression-free survival (PFS) will be assessed using iRECIST criteria (Appendix) and secondarily using RECIST criteria.

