4.3 Primary Endpoints

- Phase I: Dose-limiting toxicity (DLT), as defined in Section 7.2.
- Phase II: Progression-free survival (PFS) duration, defined as time from study registration until disease progression (scored using iRECIST⁸⁴) or death, whichever comes first.

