8.0 STATISTICAL CONSIDERATIONS

8.1 Randomization Procedure

At the time of study registration, subjects will be stratified by EGFR/ALK mutation status and disease burden and then will be randomized 1:1 between the two study arms using a modified permuted block treatment allocation scheme¹¹⁵. Block sizes of 2 (65%) and 4 (35%) will be considered. Study subjects and study personnel will NOT be blinded with respect to the randomization result.

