8.3 Phase II Primary Endpoint – Progression-free Survival

The primary study hypothesis is that treatment with FLT3 ligand, CD40 agonist antibody, and SBRT (Arm 1) will improve progression-free survival (PFS) compared to standard therapy (Arm 2). Based on published data for patients with advanced NSCLC who require treatment after several lines of standard therapy, we expect that the median PFS duration for subjects on Arm 2 will be 5 months. Based on our recent study using FLT3 ligand and SBRT and the expectation that CD40 agonist antibody will enhance treatment efficacy, we hypothesize that the median PFS duration for subjects on Arm 1 will be 10 months. This improvement is approximately equivalent to a hazard reduction of 50%. We are employing a *randomized phase II screening design*, using $\alpha = 0.20$ (wherein a p-value <0.20 indicates a positive trial). We anticipate that study accrual will take place over 24 months, and we will analyze treatment efficacy 12 months after accrual is completed. We do not expect any subjects to be lost to follow-up before the primary endpoint occurs. Based on these assumptions, our total sample size of 46 subjects yields study power of 81% using a two-sided log-rank test.

We will compare the distributions of PFS between treatment arms using a two-sided log-rank test. The rates at various timepoints (e.g., every 6 months after randomization) and median PFS durations for each arm will be estimated using the Kaplan-Meier method. Associated 95% confidence intervals (CI) will be calculated using Greenwood's formula. Cox proportional hazards models will be used to estimate the impact of study therapy on PFS duration.

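### Scheduled CT ends at one year and later imaging is left to unblinded physicians, while primary PFS is followed for 12 to 36 months, so about a fifth of expected events could be dated differently by arm

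*Combined protocol and SAP*

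**What the plan says.** - **Imaging.** Section 7.3 sets CT every 8 weeks during the first year. After that: "The surveillance imaging schedule beyond year 1 will be left to the discretion of the treating physicians but should follow current guidelines". No interval is given, and nothing requires the interval to be the same in the two arms. Both calendars (4.2.2 and 4.2.3) have their last CT column at Week 49.
- **Endpoint.** Section 4.3 defines the Phase II primary endpoint as "Progression-free survival (PFS) duration, defined as time from study registration until disease progression" by iRECIST, or death. It has no 12-month limit.
- **Follow-up.** Section 8.3: "We anticipate that study accrual will take place over 24 months, and we will analyze treatment efficacy 12 months after accrual is completed". The first subjects can therefore be followed for 36 months and the last for 12.
- **Blinding.** Section 8.1: "Study subjects and study personnel will NOT be blinded with respect to the randomization result".
- **Texts that do not agree.** Section 4.1 states 8-weekly restaging CT after study entry and gives no end. Appendix C (iRECIST) asks for assessments on a calendar schedule. In the Arm 1 calendar (4.2.2) and in 5.2.2, the schedule resets with each retreatment cycle. The Arm 2 calendar has no counterpart.
- **Analysis.** Section 8.3 has no rule for unequal or missed scans and no sensitivity analysis for scan timing.

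**The concern.** Radiographic progression is dated at the scan that shows it. If one arm is scanned at longer intervals, its progressions are recorded later and its PFS looks longer with no difference in disease. During the first year a common calendar largely prevents this. After Week 49 the interval is chosen by a physician who knows the arm, and care differs by arm: Arm 1 may be retreated, while Arm 2 may be on systemic therapy or, with limited disease, under surveillance alone (6.0). The test is at a two-sided 0.20 level ("wherein a p-value <0.20 indicates a positive trial") with 46 subjects, so a modest shift in a few event dates can matter. An imbalance could produce a false positive or hide a real effect.

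**Working it through.** **Inputs.** Section 8.3 gives the medians: "we expect that the median PFS duration for subjects on Arm 2 will be 5 months", and for the experimental arm "we hypothesize that the median PFS duration for subjects on Arm 1 will be 10 months". Accrual is 24 months, further follow-up 12 months, loss to follow-up nil, and the test a two-sided log-rank at 0.20. There are 46 subjects randomized 1:1, so 23 per arm. Exponential PFS and uniform accrual are my assumptions; the protocol states neither.

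**Reproducing the stated power.** With L = ln2/median, P(event by analysis) = 1 - [exp(-12L) - exp(-36L)]/(24L).
- Arm 1: 1 - (0.4353 - 0.0825)/1.6636 = 0.788; x 23 = 18.1 events.
- Arm 2: 1 - (0.1895 - 0.0068)/3.3271 = 0.945; x 23 = 21.7 events.
- Total 39.9. Schoenfeld: sqrt(39.86)/2 x ln2 - 1.2816 = 0.906, which gives power of 81.8%. A log-rank simulation gives 81.3%. The plan says 81%, so the assumptions fit.

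**Events after scheduled imaging.** Everyone has at least 12 months of follow-up, so P(event by month 12) = 1 - exp(-12L).

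| | Events by analysis | By month 12 | After month 12 | Share |
|---|---|---|---|---|
| Arm 1 | 18.1 | 23 x 0.565 = 13.0 | 5.1 | 28.3% |
| Arm 2 | 21.7 | 23 x 0.811 = 18.6 | 3.1 | 14.2% |
| Both | 39.9 | 31.6 | 8.2 | 20.6% |

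Counted from Week 49, the Arm 1 figure is 5.6 events (31.2%). Subjects still progression-free at month 12 number 23 x 0.435 = 10.0 on Arm 1 and 23 x 0.189 = 4.4 on Arm 2, about 14 in all. The Arm 1 share depends on follow-up: it would be 30.3% if every subject had 24 months and 38.5% if every subject had 36, and lower with back-loaded accrual.

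**Effect of unequal intervals.** These are log-rank simulations with 23 per arm, 8-weekly CT to Week 48 in both arms, and each event dated at the first scan at or after its true time. Both arms share a median of 5 or 10 months under the null. The intervals after year 1 are assumed, because the documents give none.

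| CT after year 1, Arm 1 v Arm 2 | False positive favouring Arm 1 |
|---|---|
| 8 v 8 weeks | 0.10 (nominal) |
| 12 v 8 weeks | 0.11-0.12 |
| 16 v 8 weeks | 0.12-0.14 |
| 26 v 8 weeks | 0.17-0.19 |

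Differences of about 0.01 are simulation noise; other runs at 26 v 8 weeks gave 0.16-0.18. If 30% of events are deaths, which need no scan, the 26 v 8 figure falls to about 0.14. In the opposite direction (8 weeks on Arm 1, 26 on Arm 2) and with the planned effect true, power falls from about 81% to 69-73%.

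**Using only the scheduled year.** Censoring everyone at month 12 leaves 31.6 events: sqrt(31.63)/2 x ln2 - 1.2816 = 0.668, power 74.8%. Other methods give 73.8% and 74.4%.

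**The Arm 1 reset.** Under 5.2.2 further cycles are not offered after progression within four months of a cycle, or when no active disease remains. Subjects who are progression-free with residual disease are therefore possible candidates. A reset can carry scheduled CT past one year on Arm 1 only. It can also delay a scan: if a new cycle began in Week 23, its Week 9 CT would fall in Week 23 + 8 = 31, where the first calendar has Week 25.

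**The case against.** The strongest reply has four parts.

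1. **Most information is protected.** About 80% of expected events (32 of 40) fall within the scheduled year. This stands and limits the size of the problem.
2. **Discretion is bounded by guidelines.** Section 7.3 says so, and with similar intervals the distortion is small: 12 v 8 weeks barely moves the error rate. That stands too. But no interval is stated, and a reference to guidelines does not secure equal scanning of two arms receiving different care.
3. **Section 4.1 may already close the gap.** Read alone, it continues 8-weekly CT. But 7.3 and both calendars are the more specific text and say otherwise, so the conflict has to be resolved.
4. **The documents do not show Arm 1 being scanned less.** This is correct. A reader might infer that Arm 1 subjects are mostly off active treatment after year 1, so that bias must favour Arm 1. Retreatment and its reset do not support that. They may mean denser scanning on Arm 1, while Arm 2 subjects with limited disease may be under surveillance only. The reset is still unequal ascertainment, so it leaves the direction open without removing the concern.

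A reader might also infer that the tail is where the plan expects the arms to differ most. It is not. The assumed hazard ratio is constant under the exponential model, and the PFS gap peaks at month 10 (50% v 25%), inside scheduled imaging. It is 24.6 points at month 12, 15.4 at month 24 and 7.6 at month 36.

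**Conclusion.** The concern holds in a limited form. The protocol has no common imaging calendar after Week 49 for an open-label PFS endpoint followed for up to 36 months, and its own sections disagree on whether 8-weekly CT continues. About 8 of 40 expected events (5 on Arm 1, 3 on Arm 2) fall in that period, given exponential PFS and uniform accrual. The direction of any bias is unknown. Its size rests almost wholly on the assumed intervals: negligible to small at 12 v 8 weeks, material at 26 v 8 weeks, and smaller in every case once deaths are counted. The documents do not support a claim that the primary result will be biased, or biased towards Arm 1. They do leave open a source of bias that could readily be removed. The sample size and the stated power are not in dispute.

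**What to change.** 1. Reconcile 4.1, 7.3 and the calendars in 4.2.2 and 4.2.3 so that both arms follow one identical CT calendar, counted from registration, until progression, death or the PFS data cut-off. The sponsor chooses the interval and states it; it should not be left to routine practice, which would bring the discretion back.
2. State that an Arm 1 retreatment reset does not alter the CT dates used for PFS.
3. Add to 8.3 a secondary sensitivity analysis of PFS censored at the Week 49 scan. It uses data already collected, but its power is about 73-75%, so it supports the common calendar and does not replace it.

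The cost is a few sentences and a calendar column. About 14 subjects are expected to be progression-free after year 1, and they would be imaged in any case. The sample size and the 81% power are unchanged. The downside is that a few scans may come earlier than a physician would choose.

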7.4 Quality-of-Life Assessments

Quality-of-life (QoL) will be assessed using the EORTC QLQ-C30 and EORTC QLQ-LC13. Of note, these tools are available in multiple languages. In the rare case where a study subject is not fluent in any language in which the QLQ-C30 and QLQ-LC13 are available, QoL assessments will be omitted. In cases where QoL assessments are due but cannot be completed in clinic for logistical reasons, QoL surveys may be administered over the telephone.

The EORTC QLQ-C30 and EORTC QLQ-LC13 are described in Section 2.9, and the assessment schedule is displayed in the Study Calendars (Section 4.2). The complete surveys are included in the Appendix. The statistical plans for QoL analysis are described in Section 8.3.

7.5 Physical Activity Monitoring

A commercially available fitness tracker (e.g., Garmin Vivofit, shown below on left) will be provided at no cost to the patient and placed on the patient's wrist at the time of study registration. The device will be activated and synced with a computer or mobile device, and the device will be set to show the time. Patients will be shown how to remove the device (like removing a wristwatch), in case they wish to remove it temporarily or permanently. However, patients will be asked to keep the device on continuously throughout the course of the study. The device is waterproof, so patients will not need to remove it when bathing. The device has a battery life of over one year, so patients will not need to charge it. Data will be synced automatically every time the patient enters one of the Medical Oncology or Radiation Oncology clinics using a wireless access client (shown below on right). In cases where the data is not synced automatically, a study team member will sync the data using a mobile device.

Wearable activity monitor (left) and wireless access client (right)

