4.2 Study Calendars

4.2.1 Pre-Registration and Pre-treatment Assessments

	Timing
CBC, BMP, LFTs	Within 21 days prior to study entry
Amylase, Lipase	Pre-treatment
Negative SARS-CoV-2 PCR	Within 21 days prior to study entry
PET/CT	Within 42 days prior to study entry
CT C/A/P	Within 21 days prior to study entry
QoL Assessments	Pre-treatment
Correlative Study Blood Draw	Pre-treatment ¹
CDX-301 ADA and CDX-1140 PK	Pretreatment (Arm 1 only) ¹

1. Must be obtained at least 21 days after last receipt of chemotherapy, targeted cancer therapy, immunotherapy, radiotherapy (excluding palliative radiotherapy), or major surgery.

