8.4 Secondary Endpoints and Exploratory Analyses

Overall survival (OS) rates and median OS durations will be estimated using the Kaplan-Meier method. Exploratory comparisons of OS distributions between study arms will be performed using a two-sided log-rank test and Cox proportional hazards models.

Radiographic response rates will be characterized using descriptive statistics. The clinical benefit rate (CBR) will be defined as the percentage of subjects who achieve best response of confirmed CR or PR, or stable disease (SD) for at least four months. CBR in Arm 1 and Arm 2 will be compared using chi-square testing or Fisher

exact test, as appropriate. Objective response rate (ORR) will be defined as the percentage of subjects who do not receive comprehensive SBRT who achieve best response of confirmed CR or PR. ORR in Arm 1 and Arm 2 will be compared using chi-square testing or Fisher exact test, as appropriate.

Quality-of life (QoL) will be assessed using the EORTC QLQ-C30 and EORTC QLQ-LC13. Summary statistics (mean, standard deviation, median, 25th and 75th percentiles, and range) and the mean change from baseline of linear-transformed scores will be reported for all the items and subscales of the EORTC QLQ-C30 questionnaire and the QLQ-LC13, according to the EORTC scoring manual guidelines and the. Completion and compliance rates will be summarized at each timepoint by treatment arm. Only patients with a non-missing baseline assessment and at least one non-missing post-baseline assessment will be included in the analyses.

Daily step count averages at baseline and at various timepoints after study registration will be characterized using descriptive statistics. To test the hypothesis that study therapy preserves physical function compared to standard therapy, a linear mixed effects model with random coefficients using a restricted maximum likelihood procedure will be used to model daily step count as a function of study arm, using adjustment variables such as age and gender.

Exploratory multivariable and subgroup analyses of PFS and OS predictors will be performed. Adjustment/grouping variables will include baseline disease burden, performance status, NSCLC subtype, and prior response to immunotherapy.

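### Baseline step counts effectively begin after open-label allocation, and baseline quality of life need only precede treatment, so it too may be recorded once the arm is known

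*Combined protocol and SAP*

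**What the plan says.** **Allocation.** Section 8.1: "At the time of study registration, subjects will be stratified by EGFR/ALK mutation status and disease burden and then will be randomized 1:1". On masking it says: "Study subjects and study personnel will NOT be blinded with respect to the randomization result".

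**Steps.** Section 7.5 has the tracker "placed on the patient's wrist at the time of study registration". No run-in, earlier issue or baseline window is given. Section 8.4 nevertheless summarises a baseline step average separately from averages at times after registration. It also fits a random-coefficients mixed model of daily steps on arm, adjusted for variables such as age and gender. Section 2.9 plans to use baseline activity as a prognostic factor and to compare rates of activity change between arms, expecting study therapy to preserve function.

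**Quality of life.** The Section 4.2.1 row reads "QoL Assessments Pre-treatment". In the same table the blood tests and diagnostic CT are due "Within 21 days prior to study entry", and the SARS-CoV-2 test and PET/CT also have windows ending at study entry. A further row, for drug antibodies and pharmacokinetics, is marked "Pretreatment (Arm 1 only". In Section 8.4, summary statistics and "the mean change from baseline of linear-transformed scores will be reported for all the items and subscales". The analysis set is restricted: "Only patients with a non-missing baseline assessment and at least one non-missing post-baseline assessment will be included in the analyses".

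**The concern.** A baseline is useful in a randomised comparison because allocation cannot have influenced it. Quality-of-life scores are self-reported and step counts are partly voluntary. Either may move when a subject learns, in an open-label trial, that the assignment is standard care or the experimental combination. If the baseline is taken after that moment, part of any reaction to the allocation sits in the reference value and is subtracted from what is later reported as change.

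At stake are the quality-of-life change from baseline as it will be read by arm, the use of baseline activity as a prognostic factor, and the early part of any comparison of activity trends. Patient-reported outcomes and activity are named secondary objectives (Section 1.2). The timing cannot be corrected for a subject who has already been randomised.

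**Working it through.** The plan gives no figure on this point to reproduce, so the check sets the timing rules side by side and then adds a short illustration under stated assumptions.

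**1. Steps.** Randomisation occurs at registration (Section 8.1), and first wear occurs at registration (Section 7.5). The two are one event. Even if the device goes on minutes before the allocation is drawn, the number of complete wear days before allocation is zero for every tracker participant. Any baseline daily average must come from days when the arm is known. Its length is also open, because the interval from registration to Week 1 is not stated. If that interval is assumed to be 0 to 7 days, baseline wear is 0 to 7 days, all after allocation.

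**2. Quality of life.** Section 4.2.1 uses two kinds of timing:

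- Blood tests, SARS-CoV-2 test, CT and PET/CT: tied to study entry. Section 3.1 ties the same laboratory tests to registration, and Section 7.3 calls the same imaging pre-registration, so entry and registration are the same point.
- Quality of life: tied only to the start of treatment.

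The table's pre-treatment category also holds a sample taken on Arm 1 alone. A sample can be restricted to one arm only once the arm is known, so this category extends past randomisation. A questionnaire completed between allocation and first treatment therefore complies. So does one completed before registration.

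**3. Which analyses use these baselines.** Quality-of-life change is descriptive, with no between-arm test or model specified. The step model in Section 8.4 is of daily steps on arm and is not written as follow-up minus baseline. Baseline activity and rates of change enter through Section 2.9.

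**4. Sensitivity of a change score (illustration only).** Assumptions: 46/2 = 23 subjects per arm, all with data; equal SDs; correlation ρ between baseline and follow-up of 0.5 to 0.7; no true difference at follow-up; mean baseline in one arm shifted by d SD. The documents give no SD, ρ or d.

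- Bias in the between-arm difference in change = −d.
- Standard error in SD units = √[2(1−ρ)] × √(2/23). At ρ = 0.5 this is 1.000 × 0.295 = 0.295; at ρ = 0.7 it is 0.775 × 0.295 = 0.228.
- Chance that a nominal two-sided 5% test would reject = 1 − Φ(1.96 − d/SE) + Φ(−1.96 − d/SE).

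| d (SD) | ρ = 0.5 | ρ = 0.7 |
|---|---|---|
| 0 | 5.0% | 5.0% |
| 0.1 | 6.3% | 7.2% |
| 0.2 | 10.4% | 14.1% |
| 0.5 | 39.6% | 59.1% |

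Using the shifted baseline as a covariate reduces the bias to −ρd but does not remove it: for d = 0.2 it is −0.10 to −0.14 SD. The plan specifies no such test for quality of life, so the table shows only how sensitive an informal comparison of mean changes would be.

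**The case against.** Several points against the concern are sound.

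- **Quality of life may well be collected early.** The Section 4.2.1 table covers both pre-registration and pre-treatment assessments, and sites may complete the form before registration. A reader might infer that baseline quality of life is collected after randomisation. The documents show only that this is allowed.
- **No shift is demonstrated.** A reader might infer that both baselines already carry the effect of the known arm. That is a risk in an open-label trial, and nothing in the documents shows that it occurs.
- **The analyses are not two formal change-from-baseline comparisons.** Quality-of-life change is descriptive. The step model can estimate slopes over all recorded days, so the one-for-one arithmetic does not apply to it.
- **Dropout is not a further argument.** A reader might infer that subjects who leave between learning the arm and completing the baseline form are lost because of its timing. Section 8.4 also requires a post-baseline form, which such subjects would lack anyway. An earlier baseline would not bring them into the analysis.
- **Follow-up data are unblinded too.** Moving the baseline leaves the later open-label measurements as they are.
- **Activity monitoring is optional** (Section 2.9) and excludes non-ambulatory subjects and walker users (Section 3.2). A wear period of no days is also unlikely on Arm 1, where SBRT simulation and planning come first.

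These points limit the weight of the concern. They do not change the timing: no complete pre-allocation day of steps can exist, and the quality-of-life baseline is not fixed relative to allocation.

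**Conclusion.** The concern holds in a limited form. For steps it is firm: under the written procedure any baseline average is effectively recorded after the arm is known, for every tracker participant. For quality of life it is a gap: the timing rule permits a post-allocation baseline for any of the 46 subjects but does not require one.

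The consequence is possible bias in quality-of-life change as read by arm, and in the uses of baseline activity and activity change described in Section 2.9. Its size cannot be derived from the documents. The illustration rests on an assumed shift, an assumed correlation and complete data, and it also assumes that the reaction to allocation is gone by follow-up.

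Only secondary endpoints are involved. The primary endpoints, DLT and PFS, use neither baseline. The change is worth making because it is cheap and removes an avoidable source of bias.

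**What to change.** **Section 4.2.1.** Require the baseline QLQ-C30 and LC13 after consent and before the allocation is requested, for example at the registration visit.

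**Section 7.5.** Issue the tracker at consent or screening where feasible, without delaying registration to gain wear days.

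**Section 8.4.** Define baseline steps as the complete wear days before randomisation. Flag subjects whose only baseline days fall after allocation and handle them in a sensitivity analysis, rather than discarding their baseline outright.

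**Cost.** The change is mainly wording. Some trackers and questionnaires will go to screen failures. The documents state no interval between consent and registration, so some subjects will have few or no pre-randomisation wear days. For them the step baseline stays limited, and the report should say so. The questionnaire change has almost no cost.
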